4.2 Objectives

Primary objectives:

a) To define and assess the predictive value of SARS-CoV-2 spike serology measurements for COVID-19 clinical outcomes (infection rates and disease severity) in CV people.

Secondary objectives:

- a) To evaluate the serological vaccine responses (magnitude and durability) of CV patients to bivalent or other vaccines given during the study period.
- b) To assess the functional activity of anti-spike IgG antibodies against new SARS-CoV-2 variants in CV patients during the study period.

Exploratory objectives:

- a) To evaluate alternate methods to predict COVID-19 infection/hospitalisation should antibody testing fail to predict relevant clinical outcomes (e.g. QCOVID4 score and T cell responses).
- b) To understand whether the serology vaccine response, in those with suboptimal responses to primary course, can be further enhanced with increasing doses of vaccination. \Box
- c) To assess T-cell response to emerging VoC in CV individuals.
- d) To determine the correlation between antibody and T-cell responses

Version: 2.0 26.11.2023 IRAS:325967

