5.0 Study population and eligibility criteria

5.1 Patient selection

Participants in this study will have an underlying disorder which has identified them as being clinically vulnerable. The disease and treatment groups eligible for participation (**TABLE 2, page 13**) in STRAVINSKY may alter throughout the study depending on the results from the retrospective analysis or other new knowledge/discussions such as the report from the Independent Advisory Group for COVID-19 medicines.⁵

TABLE 2. Groups eligible for participation

Group	Disease related groups (n=120-140 per group)				
1	Chronic lymphoproliferative disorders (footnote 1)				
2	Plasma cell disorders (footnote 2)				
3	Myelodysplastic syndrome (MDS) or (myeloproliferative neoplasms MPN) (footnote 3)				
4	Sickle cell disease, thalassaemia, or rare inherited anaemias				
5	Active malignancy diagnosed within 2 years of study consent (excluding non-melanoma skin cancer, non-invasive bladder cancer and localized squamous cell carcinoma of cervix)				
	(Note: participants who have received radiotherapy or systemic anti-cancer treatment within the last 26 weeks should be included in groups 18 and 19 first).				
6	Down's syndrome and learning disability				
7	Neurological diseases (Parkinson's and mult	iple sclerosis) (footnote 4)			
8	HIV				
9	Common variable immunodeficiency an prophylactic antibiotics and/or immunoglob	d secondary immunodeficiency (requiring ulin)			
10	Cirrhosis (footnote 5)				
11	Chronic respiratory conditions (footnote 6)				
12	Chronic kidney disease (CKD) stage 4-5 (foot	note 7)			
13	Diabetes mellitus (Type 1 and 2)				
14	Cardiac failure				
	Treatment-related group	Timing			
	(n=120-140 per group)				
15	Previous recipients of a solid organ transplant (SOT)	At any time			
16	Recipient of a haematopoietic stem cell transplant (HSCT)	Within 52 weeks at time of study consent			
17	Recipient of B-cell depleting treatment (APPENDIX 1 for details)	Within 52 weeks at time of study consent			
18	Recipient of systemic anti-cancer therapy e.g. chemotherapy or immunotherapy and others (APPENDIX 1 for details)	Ongoing or within last 26 weeks at time of study consent			
19	Recipient of radiotherapy	Ongoing or within last 26 weeks at time of study consent			
20	Autoimmune disease on systemic immunosuppressive* medication (APPENDIX 1 for details)	Ongoing or within last 26 weeks at time of study consent			

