6.0 Prospective study

6.1 Study design and overview

This is a multicentre prospective, observational cohort study (**FIGURE 1**). Patients will provide samples and clinical data on 4 different occasions over 12-18 months. For each of the 4 visits individuals will be allocated to be involved in the study either remotely or attend in-person.

3000 individuals will be recruited in total; for 2600 of these patients (remote cohort), their commitment to the study will be entirely remote.

400 individuals (in-person cohort) will be invited to attend a sampling appointment at one of the 4 inperson sampling sites (Birmingham, Southampton, Imperial or Oxford), for each of the 4 study visits. The aim will be to recruit between 120 and 140 individuals per disease/treatment group as detailed in **TABLE 2.**

13 | Page STRAVINSKY Protocol

^{*} This enables assessment of the primary outcome and response to bivalent vaccine. It is highly likely that policy on these licensed treatments will change, in which case we may submit an amendment to individuals receiving SARS-CoV-2 monoclonal Abs.

Informed consent and data collection will predominantly be collected online via a REDCap database. Patients and sites without access to devices or internet will be consented via telephone, the signed paper consent form will then be sent to the participant to counter sign, and they will be asked to post this back to the central study team.

Participants without access to devices to internet will also be offered face to face appointments where the patient can either be supported by the research nurse to complete the online consent form or the participant can sign a paper consent form. If paper consent forms are used, they will be transcribed/scanned into REDCap and the original paper source document will be stored at the recruiting site for the duration of the study. Any case report form (CRF) data collected face to face or via telephone will also be transcribed directly into the database by each local clinical care team. Paper CRF data and consent forms will be transcribed/scanned into REDCap. The original paper documents will be stored at the recruiting site.

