23.0 Appendix 3 Statistical analysis plan

Sample size and randomisation

We have assumed that a sample size of 3000 is feasible and that this is likely to be distributed as 750 in the "low response/no response" group and 2250 in the "normal response" group. We might then wish to estimate what difference between these two groups we could detect with 90% power. We have good estimates from previous studies over time in vulnerable populations and have therefore considered a range of infection and hospitalisation rates that might be plausible for this group. We have also considered the statistically most conservative option by setting the proportion at 50%.

In all cases, we can detect an absolute difference between groups of less than 10% and often less than 5% even for the rarer outcome of hospitalisation. These are consistent with a standardised effect sizes ranging from 0.15 to 0.36 for infection, which are consistent with small to moderate effects. The effect size for hospitalisation is less certain and ranges from 0.24 consistent with a small effect through to 1.33, a very large effect.

We consider this reassuring as it indicates that for a wide range of scenarios, we should have adequate power in the whole cohort for our primary outcome of infection and we may have power to detect a moderate effect for the rarer secondary outcome of hospitalisation, depending on the prevailing population rates and the variant of interest.

We will monitor all the assumptions that underlie these calculations at least monthly and will discuss monthly at our Trial Meeting Groups, if there are any concerns about power for key analyses.

Randomisation procedure

This is an observational cohort and participants will not be randomised. The cohort may be used in future to recruit to randomised trials and the process for selection and randomisation would be described accordingly in the associated trial protocol.

Statistical analysis considerations

Definition of analysis populations

CV groups are defined below and are derived in part from the QCOVID4 risk groups.

The Healthy Control (HC) group represent a population sampled from the PITCH Study (Protective immunity from T-cells in healthcare workers).

Baseline characteristics

At baseline the following characteristics will be described for the study cohort:

- Demographics (Age, BMI, self-reported ethnicity, sex, Index of Multiple Deprivation)

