- · Occupation, nature of work and type of personal protective equipment used during that work
- Medical conditions (self- reported)
- latrogenic immunosuppression (or within 6 months of iatrogenic immunosuppression including chemotherapy)
- · Vaccination history including COVID-19, influenza, and any test vaccines given
- · Known prior infection

Behavioural variables

If the participant self-isolated as a result of an illness in a household contact, we will collect data on the nature of that illness (when was illness, symptoms, severity, duration) and how many other household contacts were unwell.

Serological response

Time points for serological measurements: Assessment at 4 timepoints (Visit 1: baseline visit, Visit 2: before next vaccine dose, visit 3: 4 weeks post vaccine dose and Visit 4: 24-36 weeks post vaccine).

ii) 'Low' antibody range: Antibody values which lie within the lower 10th percentile of range of IgG antibody concentrations in HC following vaccine dose.

General analysis principles

- Summary statistics will include either mean, standard deviation, and/or median, interquartile range for continuous variables as appropriate to the distribution and n (%) for frequencies.
- The amount of missing data will be reported. Analysis will be of complete data and missing data will not be imputed.
- 5% two-sided level of statistical significance, with corresponding 95% confidence intervals presented where applicable.
- No adjustments for multiplicity are planned.

Planned analyses and reporting:

Primary Outcome

To assess the additive value of serological responses to CV status in predicting infection

The binary infection outcome will be captured by recording the timing and incidence rates of all infections from ≥14 days post vaccination given between Visit 2 until Visit 4 will be reported in the total combined CV groups, and by individual CV groups. We will describe the number and proportion of infections for each level of antibody response post-V3 (no, low, normal)

The primary analysis will be undertaken using a logistic regression model with infection as the outcome and antibody response post-V3 as a binary variable as the exposure. We will present odds ratios with 95% confidence intervals for the unadjusted model, as well as for a model adjusted for the baseline and behavioural variables as well as any COVID-19 therapy received in the community, preadmission and in hospital (where data available).

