Assuming serology is predictive of outcome, we will build a model to explore the predictive value of key patient data and the added value of serological results. We will explore the discrimination and calibration of a model only including baseline and behavioural variables compared to this model also including serological response. Discrimination will be determined by Harrell's C statistic and calibration will be determined by the predicted probabilities for infection. It is not possible to externally validate this model in this study; instead 1000 bootstrapped samples will be used in determining the 95% confidence intervals for the C statistic.

As a sensitivity analysis we will also consider serological response as a continuous variable. We will also consider time to first infection as a time to event outcome with death as a competing risk. This will be implemented in Stata using the *stcrreg* command. The same covariates will be included in the adjusted model as for the primary analysis. Unadjusted and adjusted analyses will present hazard ratios with 95% confidence intervals.

To assess the additive value of serological responses to CV status in predicting severe outcome We will undertake an analysis using the same modelling approach as for the primary outcome but with a composite outcome of severe infection (infection, hospitalisation or death).

Secondary Outcomes

To evaluate the serological vaccine responses of CV patients to new vaccines

28-day post vaccine (Visit 3) IgG antibody levels (BAU/ml) will be reported in HC and CV individuals. The proportion of combined and individual CV groups with no, low or normal Visit 3 antibody levels will be reported.

The median (IQR) of Visit 3 antibody levels in each CV group will be reported, alongside the values for HC.

Logistic regression models will be used to assess factors that contribute to serological response as a binary outcome with normal compared to lack of response (no/low). The model will include the baseline variables set out in **Section 5.2** and further variables may be added to the model if evidence emerges that such variable impacts on vaccine responses to vaccines. Univariable logistic regression will be used to explore the unadjusted relationship of each variable with the outcome and multivariable logistic regression will be used to explore the independent relationship of each variable with the outcome. We will report odds ratios and 95% confidence intervals for all models.

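### The vaccine-response objective concerns magnitude, but the only model of factors behind the Visit 3 response uses a normal versus no/low split, so no adjusted estimate of IgG level is planned

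*Protocol*

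**What the plan says.** Section 4.2 gives secondary objective (a) as "To evaluate the serological vaccine responses (magnitude and durability) of CV patients to bivalent or other vaccines given during the study period". Section 9.1 describes the assay as quantitative.

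Under Secondary Outcomes, Appendix 3 states that "28-day post vaccine (Visit 3) IgG antibody levels (BAU/ml) will be reported in HC and CV individuals", and that the share of each clinical group with no, low or normal levels will be given. The level itself is summarised only descriptively: "The median (IQR) of Visit 3 antibody levels in each CV group will be reported, alongside the values for HC".

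The one analysis of what drives the response is logistic regression, univariable and multivariable, of "serological response as a binary outcome with normal compared to lack of response (no/low"). Low is defined in Appendix 3 by the bottom tenth percentile of healthy controls after vaccination. The sample-size text expects 750 low or no responders and 2250 normal responders. Section 6.1 sets the group size: "The aim will be to recruit between 120 and 140 individuals per disease/treatment group".

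**The concern.** The objective asks how large the response is. The planned model answers a different question: who falls below a threshold. An odds ratio for not being normal does not say how much lower IgG is in, for example, people on B-cell depleting treatment than in the rest of the cohort, after allowing for age and vaccine history. Everyone above the cut counts as identical, and those with no response are merged with those who are low.

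Two things are at stake. First, the report would give magnitude only as unadjusted medians by group, although groups are likely to differ in age, treatment and vaccination. Second, with 20 groups of 120 to 140 people, modest differences between groups are hard to detect, and a binary outcome can make them harder.

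**Working it through.** **1. The plan's own power figure.** Appendix 3 sets out to "estimate what difference between these two groups we could detect with 90% power", meaning infection rates in 750 against 2250 people. At a 50% rate and two-sided 5%, the detectable difference is 6.8 points. In standardised form: ln[(0.5681/0.4319)/(0.5/0.5)] × √3/π = 0.274 × 0.551 = 0.151. This matches the stated lower limit of 0.15 and the stated difference of under 10%. No power, SD or expected shift is given for the vaccine-response model, so the steps below rest on assumptions.

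**2. Inputs.** From the protocol: the "5% two-sided level of statistical significance"; 750/3000 = 25% no/low; 20 groups of 120 to 140, taken as 130, so 20 × 130 = 2600 and one group faces 2600 − 130 = 2470 others. Assumed: log IgG is normal with equal SD, the group lies lower by *d* SD, and the tests are unadjusted.

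**3. Formulas.** Full scale: z = d/√(1/130 + 1/2470) = d/0.0900. Binary: choose the cut c so that the pooled share below it is 25%. Then p0 = Φ(c), p1 = Φ(c + d), and z = ln OR/√[1/(130·p1(1−p1)) + 1/(2470·p0(1−p0))]. Power ≈ Φ(z − 1.96).

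**4. Worked case, d = 0.25.** c = −0.688, p0 = 0.246, p1 = 0.331, ln OR = 0.4165, SE = 0.192, z = 2.17, power 58%. Full scale: z = 0.25/0.0900 = 2.78, power 79%.

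**5. Across shifts (130 against 2470, 25% no/low).**

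| Shift (SD) | Binary | Full scale | Loss (points) |
|---|---|---|---|
| 0.25 | 58% | 79% | 21 |
| 0.30 | 75% | 92% | 17 |
| 0.35 | 87% | 97% | 10 |
| 0.40 | 94% | 99% | 5 |
| 0.50 | 99.4% | 99.98% | under 1 |

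**6. Other settings under the same normal shift.**
- Group sizes at the ends of the protocol range, against the rest of 3000, with the cut at the 25th percentile of the rest: at 0.25 SD, 56% against 77% (n = 120) and 61% against 82% (n = 140); at 0.30 SD, 71% against 90% and 77% against 93%.
- 10% no/low, 130 against 2470, 0.30 SD: 62% against 92%.
- 50% no/low, 130 against 2470, 0.30 SD: 74% against 92%.
- A group that responds better than the rest, 25% no/low, 0.30 SD: 59% against 92%.
- Two groups of 130 compared directly, 25% no/low, 0.35 SD: 53% against 81%.

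**7. A different shape.** Suppose groups differ only in the share of non-responders: 37% in one group of 130 against 25% in the rest, with the cut midway between the two components. Simulated power is about 50% for the binary, t and rank tests when the components lie 2 SD apart. At 3 to 4 SD apart, the binary test has roughly 70–80%, the t test 65–75% and the rank test about 60%. In this pattern nothing is lost by dichotomising, and something may be gained. If the whole group is also shifted by 0.2 SD, the full-scale test regains the advantage.

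**8. Could another analysis fill the gap?** The sensitivity analysis with continuous serology belongs to the infection outcome, where antibody is the predictor. The waning analyses concern change between visits. The QCOVID4 analysis correlates titre with one score, unadjusted. None is an adjusted model of the Visit 3 level.

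**The case against.** The best defence is that the binary outcome fits the study's purpose. The same no/low versus normal split underlies the sample size, antibody response is binary in the primary analysis, and the low category is anchored to healthy controls. Asking who falls into the risk category is a sensible question. This stands, and it is why the logistic model should stay.

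Magnitude is also not ignored. Levels in BAU/ml, medians by group beside controls, rates of decline and changes between Visits 3 and 4 will all be reported. The objective is to evaluate the response and does not itself demand a model of determinants. This stands in part: description is planned, but adjusted estimation of the level is not.

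A reader might infer that dichotomising costs this analysis a fixed 17 to 21 points of power. The documents do not support that. They give no SD, distribution or expected shift, and steps 5 and 7 show that the loss can be larger, negligible or reversed. The background section describes patient responses as heterogeneous, which is compatible with a responder/non-responder mixture. Factors that split the whole cohort have ample power either way: 1500 against 1500 at 0.20 SD gives 98% even with the binary outcome.

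A reader might also infer that the cut is wrong or that the primary analysis is harmed. Neither follows. A fuller analysis plan might add the missing model, but Appendix 3 already fixes the outcome scale for this one.

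**Conclusion.** The point holds as a mismatch between objective and analysis. Objective (a) names magnitude, and the only model of factors behind the Visit 3 response discards it above and below one cut. This conclusion needs no distributional assumption.

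The power cost is conditional. With a normal shift in log IgG, 25% no/low and one group of 130 against 2470, it is 21 points at 0.25 SD and 17 points at 0.30 SD. It falls to about 10 points at 0.35 SD and under 1 point at 0.50 SD, and may disappear or change sign if groups differ only in the share of non-responders. The consequence is confined to a secondary outcome. The IgG values are kept, so nothing is lost irrecoverably, but naming the model in advance is better than adding it after the data are seen.

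**What to change.** In Appendix 3, under the secondary outcome on vaccine response, add a Visit 3 regression with IgG level as the outcome and the same covariates as the logistic model, and name it as the analysis that addresses magnitude. Two forms would serve:

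- regression of log10 IgG, with values beyond the assay limits treated as censored, reported as geometric mean ratios with 95% confidence intervals; or
- a cumulative-probability ordinal model, which ranks undetectable results lowest without assigning them a value.

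Keep the normal versus no/low logistic model beside it, because its cut matches the primary exposure. The cost is a sentence or two of text and one more model on data already collected. The one added burden is a stated rule for values outside the assay range.

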1.0 Study Summary

Title:	Stratification of Clinically Vulnerable People for COVID-19 Risk Using Antibody Testing (STRAVINSKY)
Funding Body	NIHR- National Institute for Health and Care Research
Rationale:	Although the COVID-19 vaccination program has proved extraordinarily successful, clinically vulnerable (CV) patients remain at risk of SARS-CoV-2 infection, severe COVID-19 and death. Large (inter)national studies have previously identified patient groups who generate sub-optimal immune responses to COVID-19 vaccines, and those at highest risk of severe COVID-19. Although the precise immune correlates of protection against severe COVID-19 are not defined and this may be different in different patient groups. Recent emerging data in patient groups suggest that the serological response to vaccination is a critical determinant in COVID-19 outcomes. In this study we will i) perform a retrospective meta-analysis using previous studies to enhance stratification of patient groups for clinical risk and ii) assess if SARS-CoV-2 serological responses to COVID-19 vaccines can be used to risk stratify CV people for COVID-19 clinical outcomes.
Aim & Objectives:	Primary objectives: a) To define and assess the predictive value of SARS-CoV-2 spike serology measurements for COVID-19 clinical outcomes (infection rates and disease severity) in CV people. Secondary objectives: a) To evaluate the serological vaccine responses (magnitude and durability) of CV patients to bivalent or other vaccines given during the study period 2023 onwards b) To assess the functional activity of anti-spike IgG antibodies against new SARS-CoV-2 variants in CV patients during the study period 2023 onwards c) To perform a detailed retrospective analysis using pre-existing data from large national studies that may further inform the patient groups that will be enrolled in the prospective study. Exploratory objectives: a) To evaluate alternate methods to predict COVID-19 infection/hospitalisation should antibody testing fail to predict relevant clinical outcomes (e.g. QCOVID4 score and T cell responses). b) To understand whether the serology vaccine response, in those with suboptimal responses to primary course, can be further enhanced with increasing doses of vaccination.

Study Design:

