To assess serological responses, antibody boosting, antibody waning and correlation with infection

The above analyses focus primarily on Visit 3 (4 weeks post vaccine booster). Similar analysis will be performed from antibody status at time point Visit 1, with adjustment required for time post-vaccine to Visit 1, and also vaccine type pre-Visit 1 (Wuhan or bivalent vaccine). Infection outcomes will be described up until Visit 2. Assessment of waning (rate of antibody concentration decline) will also be described between Visit 1 and Visit 2. Assessing differences between HC versus CV group, but also individual groups. Similar waning analysis will be reported between Visit 3 and Visit 4.

Descriptive changes in antibody levels between Visit 3 and Visit 4 by CV groups will also be reported.

Sponsor: University of Birmingham

Antibody binding to VOC

This analysis will be focused on samples derived from Visit 1 and at subsequent follow up points, assuming this will capture most diversity in VOC during the study duration. Antibody binding to SARS-CoV-2 WT will be compared against binding to the dominant VOCs in participants with detectable antibodies and reported as fold-change (e.g. VOC/WT) and absolute change.

Subgroup analyses

We will present the number and proportion of patients with adequate and inadequate antibody response in each disease subgroup. We will also present the number and proportion in each of these groups with COVID-19 infection and COVID-19 related hospitalisation. Provided there are sufficient numbers in each group, we will undertake exploratory analyses using the same approach as for the analysis of the primary outcome in the full cohort.

Exploratory Analyses

Evaluation of QCOVID4 risk score

i) Is the QCOVID4 score associated severe COVID-19 in our cohort? (low/med/high and quantitative analysis)

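### The exploratory subgroup analysis refits the primary model group by group with no antibody-by-group test, so it cannot show whether the antibody effect differs between patient groups

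*Protocol*

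**What the plan says.** All references are to the protocol; section 11 names its Appendix 3 as the statistical analysis plan.

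- **Subgroup analyses (Appendix 3).** Counts and proportions of antibody response, infection and hospitalisation are described for each disease subgroup. Then, on condition of sufficient numbers, "we will undertake exploratory analyses using the same approach as for the analysis of the primary outcome in the full cohort". The condition has no threshold.
- **Primary analysis (Appendix 3).** The approach to be repeated is a logistic regression of infection on binary post-vaccination antibody response. It is reported unadjusted, and adjusted for baseline and behavioural variables and COVID-19 therapy, as odds ratios with 95% intervals.
- **General principles (Appendix 3).** "5% two-sided level of statistical significance, with corresponding 95% confidence intervals presented where applicable", and "No adjustments for multiplicity are planned".
- **Groups (section 5.1, Table 2).** Rows 1-14 are headed "Disease related groups (n=120-140 per group"; rows 15-20 are treatment-related groups of the same size.
- **Rationale (section 1.0).** It notes that "the precise immune correlates of protection against severe COVID-19 are not defined and this may be different in different patient groups".

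No antibody-by-group interaction or heterogeneity test is mentioned. The only nested-model comparison concerns adding serology to the QCOVID4 score.

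**The concern.** The rationale allows that protection may work differently in different patient groups, recruitment fills groups of equal size, and results are to be reported by group. Readers will therefore compare the groups. Separate regressions do not support that comparison. A significant result in one group and a non-significant one in another is not evidence that the two odds ratios differ, and in groups of about 130 such a contrast is expected even when they are equal.

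At stake is the reading of the group-level results. A uniform antibody effect could be taken for a patchwork of groups where serology works and groups where it does not. A real difference between groups would have no test addressed to it.

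**Working it through.** **1. The plan's own figure.** Appendix 3 asks "what difference between these two groups we could detect with 90% power", with 750 low/no responders against 2250 normal responders. Using the pooled-variance two-proportion formula at 5% two-sided, the detectable difference is 6.8 points at a 50% rate, 6.4 at 30%, 5.7 at 20%, 4.4 at 10% and 3.4 at 5%. At 50% the odds ratio is 1.32, and ln(1.32) × √3/π = 0.15. This agrees with the plan's differences below 10 points, often below 5, and with its lowest standardised effect for infection, 0.15. The plan states no power for subgroups.

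**2. Inputs for one group.** N = 130 (middle of 120-140). The 25% low-response share is the plan's overall split, 750/3000; applying it within each group is my assumption. It gives 33 low and 97 normal responders. Infection in normal responders (p0) of 10%, 20% or 30% is also assumed, because the plan's rates are not shown. I further assume no dropout, unadjusted models and Wald tests.

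**3. Power in one group.** With p1 = OR·p0/(1 − p0 + OR·p0):

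SE(ln OR) = √[1/(33·p1(1−p1)) + 1/(97·p0(1−p0))]; power ≈ Φ(ln OR/SE − 1.96).

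Example, OR 2 and p0 = 0.20: p1 = 0.333; SE = √(0.136 + 0.064) = 0.448; power ≈ Φ(0.693/0.448 − 1.96) = Φ(−0.41) = 0.34.

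| True OR, same in all groups | Formula, p0 = 10 / 20 / 30% | Simulated range |
|---|---|---|
| 1.5 | 10 / 14 / 16% | 11-17% |
| 2 | 23 / 34 / 39% | 24-39% |
| 3 | 55 / 72 / 75% | 54-77% |

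**4. A mixed picture from one common effect.** With k groups and per-group power π, the chance of at least one significant and at least one non-significant group is about 1 − (1−π)^k − π^k.

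- OR 1.5: from 1 − 0.894^14 = 0.79 (k = 14, π = 0.106) to 1 − 0.833^20 = 0.97 (k = 20, π = 0.167).
- OR 2, least favourable case for a mix: 1 − 0.764^14 = 0.977 (k = 14, π = 0.236).
- OR 3, least favourable case: 1 − 0.764^14 = 0.977 (k = 14, π = 0.764, so the term that matters is all 14 significant).

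Simulation (20,000 runs per setting) gives about 79-97% at OR 1.5 and over 97% at OR 2-3. In the same homogeneous settings, a single heterogeneity test (Cochran's Q) rejects in only about 1-4% of runs.

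**5. No effect anywhere.** In the direction of low antibody with more infection, the nominal chance of at least one significant group is 1 − 0.975^14 = 30% or 1 − 0.975^20 = 40%. Simulated Wald tests give about 32-44%.

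**6. Would correcting the separate fits help?** Bonferroni over 20 groups tests each at 0.05/20 = 0.0025. Power in a group for the whole-cohort detectable difference then falls to about 1-1.6%. Correction would only make the separate fits less informative.

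**The case against.** The analyses are labelled exploratory and run only if numbers suffice; the power claim is confined to the whole cohort; results are odds ratios with intervals; and nothing says that a group will be declared predictive on its p-value. All of this is correct and limits the weight of the point. It does not remove it. The sufficiency condition has no threshold, and an exploratory label does not turn tests of OR = 1 into a comparison of odds ratios. Even if only five groups of 130 were fitted, OR 2 with π = 0.34 would give a mixed picture in 1 − 0.66^5 − 0.34^5 = 87% of studies.

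A reader might infer more than the document supports:

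- **That some group will usually look predictive by chance.** The nominal 1 − 0.95^20 = 64% counts both directions and all 20 groups. The expected direction gives about 32-44%, and the text says disease subgroup, which may mean 14 groups.
- **That most true effects will be missed.** This holds up to about OR 2. At OR 3, per-group power is 54-77%.
- **That the study exists to tell patient groups apart.** The prospective objectives concern predictive value in clinically vulnerable people. Differences between groups appear in the rationale and the reporting; prediction across groups is an objective of the retrospective meta-analysis.
- **That the lack of multiplicity adjustment is the fault.** It is disclosed, and is common for exploratory analyses.

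A separate analysis plan could add an interaction test. Appendix 3 is itself presented as the analysis plan, however, and it fixes the method of separate fits, so this carries little weight.

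**Conclusion.** The point holds as a criticism of method in a conditional, exploratory analysis. The planned fits do not address whether the antibody effect varies between groups, and under a common effect they will nearly always suggest that it does: a mixed picture in about 79-97% of studies at OR 1.5 and over 97% at OR 2-3, for 14 or 20 groups. Per-group power is low for modest effects and fair at OR 3. The primary whole-cohort analysis is unaffected.

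The figures rest on the assumed 25% low-response share in every group, 10-30% infection in normal responders, complete data and unadjusted models. Actual shares will vary by group. Missing Visit 3 samples would lower power further, and so would covariate adjustment with about 26 infections per group (20% of 130).

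**What to change.** In the Subgroup analyses paragraph of Appendix 3, replace the separate regressions by one full-cohort logistic model with clinically vulnerable group, antibody response and an antibody-by-group term.

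- Report the global interaction (heterogeneity) p-value, and the group odds ratios with 95% intervals from that model. Partial pooling through a random slope is optional.
- Keep the descriptive counts per group as planned.
- State that no claim will be made for a group from its own p-value.
- Say whether disease subgroup means the 14 disease groups or all 20.

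No multiplicity correction of separate fits is needed.

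The cost is a change of wording and one model, with no new data. There are two downsides to state in the plan: the global interaction test has low power, so a non-significant result does not show that the groups are alike; and partially pooled estimates, if used, are drawn toward the overall odds ratio.
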